**Outcome variables**

- Apico-coronal changes of the peri-implant mucosal zenith from prosthesis delivery to one year (Primary).
- Submarginal bucco-lingual soft tissue thickness in the peri-implant transition zone relative to a fixed reference point.
- Quantification of the topographical and volumetric features of the interface between the peri-implant mucosa and the transition zone.
- Keratinized mucosa width in an apicocoronal direction at the midfacial aspect of the implant site.
- Gingival Index (GI), Plaque Index (PI), Bleeding on probing (BOP) and probing pocket depths (PPD) at six sites (disto-lingual, mesio-lingual, mid-lingual, mesio-buccal, disto-buccal, mid-buccal).

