study reported seven implant fixtures (13.0%) displaying mid facial recession of <0.5mm at 12 months, and 29 patients (53.7%) exhibiting a vertical gain of keratinized soft-tissue from baseline to 12 months. No implant sites demonstrated recession of >0.5mm at 12 months. Thus, a statistically significant gain in keratinized soft tissue on the mid-facial aspect of the experimental abutments with inwardly narrowed profiles at the transmucosal level was observed. The authors attributed the gain in keratinized soft tissue height to three principle factors afforded by the abutment's concave secondary plane:

1. The circumferential concavity created a profile that enabled a localized thickening of the soft-tissues to occur, relative to a divergent abutment.
2. The curved concave profile allowed for an increase in length of the soft tissue-to-abutment interface, meaning that a greater biological seal could be obtained for the same vertical height of the implant platform relative to the gingival margin.
3. The circumferential concavity enabled a greater amount of connective tissue attachment to form, enabling a more robust seal to be established.

In a 2009 study, Redemagni et. al (8) examined 28 patients treated with 33 XiVE implant fixtures restored with concave facial emergence profile abutments in the anterior maxillary region for a mean of 20.4 months. For this study population, a mean of 0.0mm (range of -0.5mm to +1.0mm) of labial mucosal recession was observed. The authors' observations agreed with Rompen's findings that concave facial emergence designs were consistent with facial soft tissue stability, most likely due to increased connective tissue volume in the apical transition zone.

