The investigators propose to utilize a standardized digital stereotactic photography setup (Canfield Dental Camera, Canfield Imaging Systems, Fairfield, NJ) (Fig. 3) from the date of abutment/restoration delivery, and subsequently at 1, 3, 6, and 12 months to accurately document the dynamics of the facial soft tissue. Use of standardized stereotactic digital photography will enable greater accuracy and precision with regard to soft-tissue zenith measurements over time (Fig. 4). This technique is currently being employed as part of a Dentsply Implants-sponsored prospective, randomized, multicenter study called “PROOF” (YA-OSS-0003). After photographic documentation is completed for all time points, a digital software analysis program such as NIH Image J (National Institutes of Health, Bethesda, MD) can be utilized to measure length changes at the mid-facial gingival crest to any desired scale (i.e., tenths of a millimeter or pixels). At recall visits, bucco-lingual peri-implant mucosal thickness will be measured from a fixed reference point, as well as other clinical parameters that include: Plaque Index (PI), Gingival Index (GI) (10), probing pocket depth (PPD), bleeding on probing (BOP) and keratinized mucosa width (KMW) using a UNC-style probe (Fig. 6). These data will be used along with the photographic data to extrapolate the potential role that concavities in the abutment transition zone may play in preserving or enhancing facial soft tissue dynamics.

FIGURES:

[figure not shown]

Fig 6a Mesiodistal section of FM group implant.

Fig 6b Mesiodistal section of CMG group implant.

Fig 6c Mesiodistal section of SA group implant.

(Fig. 1) Histological sections of FM (Fig. 6a), CMG (Fig. 6b), and SA (Fig. 6c) transmucosal profiles, demonstrating superior quantity of connective tissue for CMG configurations.

(Fig. 2) Proposed configurations of the submucosal transition zones of either linear divergent (left) or concave (right) Atlantis™ abutments. Relative lengths of either the divergent (Ld) or concave (Lc) can be calculated

[figure not shown]
during the design/manufacturing process. The volumetric space (x) provided for by the experimental concavity can also be extrapolated from the Atlantis™ software.

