### Average Bucco-Lingual Thickness

[figure not shown]
[figure not shown]

Table 12: Keratinized Mucosa Width

Treatment	Mean	SD	Min	Max	Median	N
Baseline						
Concave	3.307	1.8425	0.0	9.0	3.0	31
Divergent	2.704	1.1373	0.0	5.0	3.0	27
1 Month						
Concave	3.936	1.7212	2.0	9.0	3.5	31
Divergent	3.407	1.1522	0.0	5.0	3.5	27
3 Months						
Concave	4.177	1.6711	2.0	9.0	4.0	31
Divergent	3.620	0.8930	2.0	5.0	4.0	25
6 Months						
Concave	4.067	1.6439	2.0	8.0	3.5	30
Divergent	3.478	0.9946	1.5	5.5	3.5	25
12 Months						
Concave	4.035	1.8609	1.0	9.0	3.5	29
Divergent	3.560	1.0832	1.0	5.5	4.0	25
Average						
Concave	3.878	1.6421	1.4	8.4	3.4	31
Divergent	3.257	1.0644	0.0	4.7	3.3	27

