### Average Keratinized Mucosa Width

### Statistical Analyses

We used mixed models to analyze the effect of time and treatment on each of the variables of interest. The results are summarized in tables below.

Canfield values, bleeding on probing, plaque index, gingival index, and keratinized mucosa width changed significantly over time. Canfield values, bleeding on probing, plaque index, and keratinized mucosa width have a curved relationship with time. Treatment alone is not significant in any model, but is significant in

an interaction with time in bucco-lingual thickness; the effect of treatment on this measure is significantly different across time points.

Table 13: Canfield Model

	P-Value
Time	< .001
Time 	< .001
Treatment	0.853

Table 14: Probing Depth Model

	P-Value
Time	0.096
Treatment	0.307

Table 15: Bleeding on Probing Model

	P-Value
Time	0.0791
Time 	0.0282
Treatment	0.9170

Table 16: Plaque Index Model

	P-Value
Time	0.1640
Time 	0.0436
Treatment	0.9880

Table 17: Gingival Index Model

	P-Value
Time	0.00146
Treatment	0.40900

Table 18: Bucco-Lingual Thickness Model

	P-Value
Time	0.0744
Time 	0.1440
Treatment	0.6740
Treatment:Time	0.0169
Treatment:Time 	0.0359

Table 19: Keratinized Mucosa Width Model

	P-Value
Time	< .001
Time 	< .001
Treatment	0.106

Over time, there was not a significant relationship between bucco-lingual thickness and any of Canfield values, probing depth, bleeding on probing, or keratinized mucosa.

Table 20: Canfield and Bucco-Lingual Thickness

	P-Value
Time	< .001
Time 	< .001
Thickness	0.178

Table 21: Probing Depth and Bucco-Lingual Thickness

	P-Value
Time	0.0928
Thickness	0.6720

Table 22: Bleeding on Probing and Bucco-Lingual Thickness

	P-Value
Time	0.1190
Time 	0.0381
Thickness	0.7340

Table 23: Keratinized Mucosa Width and Bucco-Lingual Thickness

	P-Value
Time	< .001
Time 	< .001
Thickness	0.705

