### Baseline-adjusted Analysis

We adjusted for baseline values of Canfield, bucco-lingual thickness, and keratinized mucosa width by subtracting the baseline from each subsequent measure, since any differences at delivery for these variables should be due to chance and not implant type.

Table 24: Canfield (Adjusted for Baseline)

Treatment	Mean	SD	Min	Max	Median	N
1 Month						
Concave	-0.152	0.180	-0.74	0.09	-0.15	29
Divergent	-0.176	0.302	-0.73	0.73	-0.14	25
3 Month						
Concave	-0.160	0.242	-0.89	0.54	-0.15	29
Divergent	-0.185	0.329	-0.91	0.71	-0.17	25
6 Month						
Concave	-0.171	0.280	-0.99	0.54	-0.15	29
Divergent	-0.207	0.323	-0.74	0.72	-0.23	25
12 Month						
Concave	-0.174	0.278	-0.84	0.54	-0.20	29
Divergent	-0.238	0.362	-0.85	0.75	-0.31	25

Average Canfield (Adjusted for Baseline)

[figure not shown]

Table 25: Bucco-Lingual Thickness (Adjusted for Baseline)

Treatment	Mean	SD	Min	Max	Median	N
1 Month						
Concave	-0.218	1.138	-3.5	2.0	0.0	31
Divergent	-0.056	1.204	-3.5	2.0	0.0	27
3 Months						
Concave	-0.347	1.030	-3.0	1.5	0.0	31
Divergent	0.120	1.244	-2.5	3.0	0.0	25
6 Months						
Concave	-0.258	1.175	-4.0	2.0	0.0	30
Divergent	0.200	1.199	-3.5	2.0	0.5	25
12 Months						
Concave	-0.267	1.250	-3.5	2.0	0.0	29
Divergent	0.020	1.036	-2.0	2.5	0.0	25

Average Bucco-Lingual Thickness (Adjusted for Baseline)

[figure not shown]
[figure not shown]

Table 26: Keratinized Mucosa Width (Adjusted for Baseline)

Treatment	Mean	SD	Min	Max	Median	N
1 Month						
Concave	0.629	1.056	-1	4.0	0.5	31
Divergent	0.704	0.737	0	2.0	0.5	27
3 Months						
Concave	0.871	1.162	-2	4.0	1.0	31
Divergent	0.800	0.890	-1	2.5	1.0	25
6 Months						
Concave	0.717	1.031	-1	4.0	0.5	30
Divergent	0.658	0.863	-1	2.0	0.5	25
12 Months						
Concave	0.672	1.144	-3	4.0	1.0	29
Divergent	0.740	0.914	-1	2.0	1.0	25

Average Keratinized Mucosa Width (Adjusted for Baseline)

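### The reported time effect for keratinized mucosa width is almost wholly a step between Baseline and month 1, and Baseline belongs in the model as a covariate, neither as an outcome visit nor by subtraction

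*Combined protocol and SAP*

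**What the plan says.** The protocol's Outcome variables section lists "Keratinized mucosa width in an apicocoronal direction at the midfacial aspect of the implant site". Statistical methods plans changes relative to baseline at four recalls for the primary outcome, and an analogous analysis for quantitative secondary outcomes, with keratinized width as its example.

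The results report (dated October 1, 2019) analyses width twice.

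- **First Statistical Analyses section:** "Canfield values, bleeding on probing, plaque index, gingival index, and keratinized mucosa width changed significantly over time". The text adds that the course for width is curved. Table 19 gives Time and Time² both p < .001 and Treatment p = 0.106.
- **Baseline-adjusted Analysis:** "We adjusted for baseline values of Canfield, bucco-lingual thickness, and keratinized mucosa width by subtracting the baseline from each subsequent measure", on the ground that "any differences at delivery for these variables should be due to chance and not implant type". Table 26 tabulates the changes. Table 29 gives Time p = 0.694 and Treatment p = 0.952.

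The Baseline rows of Table 12 (mean, SD, minimum, maximum, median, N) are "Concave 3.307 1.8425 0.0 9.0 3.0 31" and "Divergent 2.704 1.1373 0.0 5.0 3.0 27". The report does not link the two time results, and it does not set width change against the photographed zenith change.

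**The concern.** Keratinized gain is central to the protocol's rationale: the cited pilot study of concave abutments is summarised as "29 patients (53.7%) exhibiting a vertical gain of keratinized soft-tissue from baseline to 12 months". A reader who sees a significant curved time course and changes of 0.6-0.9 mm in Table 26 may take it that keratinized tissue went on growing around both abutments during the year. If the change is one early step, common to both arms and larger than the margin movement in the photographs, the sentence needs to say so.

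The handling of Baseline also affects the arm comparison. The arms differ by 3.307 - 2.704 = 0.603 mm at Baseline. Table 19 carries that difference inside its treatment term. Subtraction over-corrects for it whenever the slope of recall width on Baseline width is below 1.

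**Working it through.** **Inputs.** Width: Tables 12 and 26. Zenith: Tables 1 and 24. Canfield units are not printed and are taken as mm.

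**1. Reproducing the change tables.** Visit mean minus baseline mean gives all eight Canfield cells of Table 24 within 0.001. For width, the three cells with no loss of subjects agree within 0.001 (concave months 1 and 3, divergent month 1). The other five differ by 0.04-0.12, as expected if change is computed only in subjects still seen.

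**2. Where the width change sits.**

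- Concave: 0.629 / 0.672 = 94% of the month-12 change is present at month 1; net later movement is 0.672 - 0.629 = 0.043 mm.
- Divergent: 0.704 / 0.740 = 95%; net later movement is 0.740 - 0.704 = 0.036 mm.
- The step alone has t = 0.629 / (1.056/√31) = 3.3 and 0.704 / (0.737/√27) = 5.0, enough to produce significant time terms once Baseline is an outcome visit.
- The recalls are not flat: concave change is 0.629, 0.871, 0.717 and 0.672 mm at months 1, 3, 6 and 12.

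**3. Width change beside zenith shift.** Gap = width change minus absolute Canfield change.

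| Month | Concave | Divergent | Zenith as share of width (C / D) |
|---|---|---|---|
| 1 | 0.629 - 0.152 = 0.477 | 0.704 - 0.176 = 0.528 | 24% / 25% |
| 3 | 0.871 - 0.160 = 0.711 | 0.800 - 0.185 = 0.615 | 18% / 23% |
| 6 | 0.717 - 0.171 = 0.546 | 0.658 - 0.207 = 0.451 | 24% / 31% |
| 12 | 0.672 - 0.174 = 0.498 | 0.740 - 0.238 = 0.502 | 26% / 32% |

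Pooled over arms by N, the gap is 0.50, 0.67, 0.50 and 0.50 mm. The paired correlation is not reported. At month 12 the 95% interval is 0.21-0.79 with zero correlation and 0.14-0.86 at the least favourable correlation. The other pooled intervals also exclude zero; some single-arm intervals touch it at the least favourable correlation.

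**4. Effect of how Baseline is used.** Raw arm differences in Table 12 are 0.603 mm at Baseline, then 0.529, 0.557, 0.589 and 0.475. Table 19's treatment term, with no interaction, therefore largely restates the Baseline difference.

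For the covariate analysis, the covariance of Baseline and recall follows from the SDs: cov = (s0² + s1² - s_change²)/2. At month 12:

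- Concave: (3.395 + 3.463 - 1.309)/2 = 2.775. Divergent: (1.293 + 1.173 - 0.835)/2 = 0.816.
- Pooled slope b = (28×2.775 + 24×0.816) / (28×3.395 + 24×1.293) = 97.3/126.1 = 0.771.
- Residual sum of squares: 125.1 - 97.3²/126.1 = 50.1, against 56.7 for change scores, a cut of 12%.
- Baseline difference in subjects still seen: (4.035 - 0.672) - (3.560 - 0.740) = 0.543 mm.
- Shift in contrast: (1 - 0.771) × 0.543 = 0.124 mm, from 0.672 - 0.740 = -0.068 to +0.056 mm.
- SE = √[(50.1/51) × (1/29 + 1/25 + 0.543²/126.1)] = 0.28.

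The same steps at months 1, 3 and 6 give slopes 0.780, 0.663 and 0.706; variance cuts 14%, 25% and 23%; shifts 0.133, 0.164 and 0.156 mm; adjusted contrasts 0.06, 0.24 and 0.22 mm with SEs 0.23, 0.25 and 0.23. Every adjusted contrast is below one SE.

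**The case against.** The best defence is that the report already gives the answer. Table 29 uses recall visits only and finds no time effect, and subtracting a constant per subject leaves within-subject time contrasts unchanged. A covariate model should give much the same time result. That stands: the covariate serves the arm contrast and its precision, and the time sentence needs rewording more than new evidence. One limit is that Table 29 lists only linear Time, which is a poor test of a rise to month 3 followed by a fall.

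It is also fair that the Table 19 sentence reports its model correctly, that the report credits neither abutment with keratinized gain, and that width is not named among the protocol's objectives.

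A reader might go further and infer that the Baseline reading was unscheduled or faulty, so that the step is an artefact. The documents do not support that:

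- The protocol sentence "At recall visits, bucco-lingual peri-implant mucosal thickness will be measured from a fixed reference point, as well as other clinical parameters that include" names width at recalls, but it also covers bucco-lingual thickness, which Fig. 6 marks at the Permanent Crown visit. It does not exclude a delivery reading. Fig. 6 as read shows no width row at any visit.
- Statistical methods implies a baseline width by planning an analogous change analysis.
- Width has two borders, so apical-border movement could account for the gap. Width is read with a probe and the zenith from photographs.
- The zenith series also steps early: 87% (concave) and 74% (divergent) of its 12-month change is present at month 1.
- The excess does not all arise by month 1. In the concave arm it grows from 0.477 to 0.711 mm by month 3.

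**Conclusion.** The point holds as one of analysis and reporting. The significant time effect in Table 19 rests on a Baseline-to-month-1 step of 0.63/0.70 mm, with about 0.04 mm net movement per arm afterwards. The step exceeds the photographed margin shift by about 0.5-0.7 mm in both arms, so it is not evidence for either abutment. Its cause cannot be settled from the tables.

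The gap compares magnitudes and assumes that a falling Canfield value means coronal movement, which the documents do not state. If it means recession, the pooled mismatch is larger, 0.83-1.01 mm. The samples also differ slightly (31/27 for width and 29/25 for Canfield at month 1).

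Using Baseline as a covariate shifts the arm contrast by about 0.12-0.16 mm and cuts residual variance by about 12-25%. These figures apply full-sample Baseline SDs to the subjects still seen. They do not suggest that an abutment difference has been missed.

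**What to change.** 1. Analyse width at the four recall visits with Baseline width as a covariate, replacing Baseline as an outcome visit (Table 19) and subtraction (Table 29). Let the time terms allow a non-linear course, for example visit as a factor.
2. Reword the first Statistical Analyses section along these lines: width rose between Baseline and month 1 in both arms and showed no significant change across the recalls (confirm from the refit); the step is larger than the zenith shift and common to both arms, so it does not favour either abutment.
3. Tabulate width change beside zenith change in subjects with both, and state the Canfield sign and reference point and when and how Baseline width was taken.
4. Keep the Baseline-to-month-1 change as an observed result. Withdraw it only if source records show that the Baseline reading was not comparable with the recalls.

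The cost is one refitted model, one table from data already held and a few sentences. The time result for width will read less strongly than it does now.

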### Statistical Analyses

We used mixed models to analyze the effect of time and treatment on each of the variables of interest. The results are summarized in tables below.

For Canfield, time was marginally significant but treatment was not. For bucco-lingual thickness, there were significant interactions between treatment and both time and time: the effect of treatment changed over time. In the keratinized mucosa model, neither time nor treatment were significant.

Table 27: Canfield Model (Adjusted for Baseline)

	P-Value
Time	0.0571
Treatment	0.6130

Table 28: Bucco-Lingual Thickness Model (Adjusted for Baseline)

	P-Value
Time	0.5680
Time 	0.5760
Treatment	0.8330
Treatment:Time	0.0465
Treatment:Time 	0.0510

Table 29: Keratinized Mucosa Width Model (Adjusted for Baseline)

	P-Value
Time	0.694
Treatment	0.952
